**Protection against risk**

We will take the following steps to protect against risks associated with this research project:

*We will minimize the risk of breach of confidentiality.*

Risk of social or legal consequences as a result of disclosure of IPV within the past year will be dealt with in several ways. We will minimize the potential risks due to loss of confidentiality by strictly adhering to the guidelines for research outlined by Women and Infants Hospital IRB, Rhode Island state law and the DHHS Federal Policy for the Protection of Human Subjects (45 CFR Part 46 Subpart D). As described in the previous section, there will be full informed phone or in-person consent prior to participation in the study (a two-part consent process). Participant data will be encrypted in transit between user and server. No identifying information will be entered into the ACASI. The use of a linking table will provide the participant with confidentiality as the link between the participant code number and name will be kept in a password protected file on password protected computer. Lastly, potential participants will be informed of the situations in which they may not be protected under the Certificate of Confidentiality. No information about participants will be released without their permission or where required by law.

Possible distress due to sensitive items will be noted clearly in the informed consent information sheet (for screening) and in the written informed consent form (for participants). All participants will be told that they can skip any question or quit at any time if they become uncomfortable. To further address possible distress due to sensitive items, participants will be periodically asked by the research assistant (RA) if anything the RA has asked or done is making them feel upset right now. For both the online intervention and in-person computer-delivered intervention, the research assistant will contact the participant after 40 minutes, the time it takes to watch the intervention and inquire if anything in the intervention distressed her. At a minimum, all participants indicating some distress will be given a list of referral options. If in treatment women will be encouraged to contact their mental health provider.

*We will minimize the risk of study-related partner violence.*

Participants who return to or continue to have contact with their abuser may be at increased risk for abuse if he or she were to find out about the woman's participation in the research project. The measures suggested by Sullivan and Cain (2004) will be taken to maximize participant safety throughout the research. The office research line is a number that is blocked and the line will be answered, "Women and Infants Program," and partner violence will never be mentioned. Likewise, staff work cell will be answered with Women and Infants Program. When potential participants are contacted through text or email using contact information obtained from EPIC, RAs will let potential participants know that they are from Women and Infants Hospital and that they will be calling them and provide their study cell number. If reference to the screener is made in text or email, it will be referred to as a brief women's health survey. Details of the research are not provided to anyone other than the actual participant. During each contact, participants will first be asked if it is a safe time to speak. Safe contact for follow-up assessments will be negotiated at each stage of the research. Both written and verbal contacts will be vague and never mention that the research involves partner violence. Safety plans will be negotiated up front (e.g., code words, cover story for reason for interview) if ever the abuser were to interrupt a phone call or assessment or –if during a call to the participant there is noise and concern for the safety of the participant, research staff will ask the participant if she is safe and ask if the police needs to be contacted. If participant says yes to police being contacted, the research staff will call the police. Any handouts with important information (e.g., hotline numbers) will be available in wallet size copies without any reference to the study or name of organization. Participants' safety contact information, including the Locator Form, will be updated and confirmed at each assessment to determine if the

contact information they previously provided is still accurate and safe. Initial contact information collected prior to screening in the contact form will be placed in a secure, password protected excel sheet the same day. Contact forms will then be shredded by the RA. After one month the contact information will be deleted from the protected excel sheet. Participants will be given contact information for the research team and asked to let us know if the contact information they provided is no longer safe. All research personnel (i.e., PI, research assistant, interventionists) will be able to call the PI for advice on cases where there is a concern for the safety of the respondent and the PI will be available at all times by pager. Research staff will contact PI, if there are any safety concerns.

The online intervention will be sent to a secure email as a link (i.e., URL) to the intervention. The link will not contain any wording that could reveal the nature of the intervention/study. The link will become inactive once the intervention is completed. Women can hit the stop button at any time during the intervention and it will stop immediately. Women can also click an escape button during the intervention that will redirect her to the Google search page. The link (URL) can then be sent again and the participant can continue with the intervention from the place where she stopped. If the woman chooses to view the online intervention remotely through their iPhone or iPad, they will have to download the CIAS app from the app store to open the link for the intervention. The app itself has as its only description as "Medical" and "Wayne State University". The image of the app has a yellow heart with a stethoscope. When the participant uses the emailed link to view the intervention, the CIAS app will automatically open. This is the only time the CIAS app will show information about the study. If another person were to open the app at another time, they would be unable to see the completed intervention. Although the proposed intervention seeks to help a woman to develop strategies for keeping herself safe, it is possible that a woman who participates in the study might be at increased risk of partner violence because of increased assertiveness. At each follow-up assessment, our assessment of community resource use will ask about participants' visits to emergency rooms, health professionals, etc. The Composite Abuse Scale (CAS) will be administered to monitor abusive experiences in the context of a woman's relationship since the last assessment. Women will be asked at follow up sessions about any instances of hospitalizations, emergency room visits, life threatening threats of IPV, rape, or sexual assault to better gather information regarding any potential adverse events to report to the Data Safety Monitoring Board (DSMB) (see section D5 below for more details), which will monitor these events.

For the duration of the study, if a woman discloses that she is in an abusive relationship, she will be provided with the battered women's crisis line for emergencies, referrals to battered women's shelters, and told how to obtain a restraining order. If the partner of the participant is also abusing her child[ren], the research staff person involved will let the woman know that she has a choice to make, either she herself will call child welfare or the research staff will report the concern. She will be reminded that she as the mother is responsible for protecting her child[ren] and if her partner hurts them and she fails to call child welfare or the police, she could be charged with neglect and her children could be taken away. However, the woman must determine if calling child welfare herself will place her at further risk from the abuser. The research personnel involved will also remind the woman that if she calls herself, child welfare is more likely to view the woman favorably under these circumstances. The research personnel involved will provide the woman with the relevant phone number/s. The research personnel involved will let the woman know that let she will be calling child welfare herself because it is the law. This same procedure will be followed for any other case of suspected child abuse.

*Potential benefits of the proposed research to the subjects and others*

The potential benefits to women participating in this study include participants' increased awareness of resources for IPV. Half of the participants in this study will not receive any form of intervention, and thus are unlikely to receive any direct health benefit; however, women in both conditions will receive a list of referrals and community resources for IPV. Furthermore, the treating mental health providers of women who screen positive for IPV will (with the women's consent) be provided a print-out of women's survey responses. Half of the participants will receive a brief intervention designed to increase the likelihood of self-change and/or obtaining resources for IPV.

We believe that the risks to participants in this study are very low, particularly given the lack of connection between identifying information and data. We believe that the risks that are present are justified given the tremendous potential of this research to produce a replicable and low-cost motivational intervention that is appropriate for this group. Such an intervention, then, could potentially be presented to unprecedented numbers of persons in a way that is financially and logically feasible, potentially leading to beneficial effects for large numbers of women as well as their infants.

#### 4. DATA MANAGEMENT

##### **Adequacy of Sample Size**

The primary purpose of pilot studies is to develop interventions and test feasibility/acceptability of interventions and research procedures and sample size guidelines for treatment development from Rounsvaile and colleagues[76] recommend 15 to 30 participants per cell. A trial of such size is not adequately powered to detect between group differences. Although it can be used to suggest the potential promise of the intervention and associated effect sizes, we are well aware that these effect size estimates have large standard errors, and we primarily aim to find a pattern of results that is supportive of the experimental treatment. With baseline data from 50 participants in intent to treat analyses (about 25 per condition), we would only have statistical power adequate (.80) to detect large effects ( $d = .81$ ) with alpha of .05. Therefore, our primary emphasis will be on examining the direction of effects and the range of effect sizes for differences between conditions. All estimates of effect size resulting from this study will include 95% confidence intervals.

**Data Analysis:** Descriptive statistics will be calculated to summarize baseline characteristics for the full cohort and by intervention arm. Quality inspection will be carried out periodically to screen for missingness and data anomalies, and entry error. T-tests and chi-square-tests will be used to compare study arms with respect to demographic characteristics, IPV relationship variables, and baseline measures of frequency of IPV. Any identified confounders with  $p \leq 0.05$  will be included in major subsequent analyses.

**Site Differences:** In the preliminary analyses, participants from the two sites will be compared on all demographic and background information. We will also check for site effects with each specific hypothesis by including site as a fixed effect factor in the analysis. Site main effects and, as appropriate, interactions of site with relevant factors will be included. If site differences (and the interactions) are non-significant, this factor will be removed. Including site as a fixed effect and assuming an equal distribution of participants between sites and by treatment within each site will not change the overall sample size needed. However, the study may lack power to detect a site-by-treatment interaction unless the difference is large. Powering the study to detect the expected treatment effect separately by site is not feasible and would elevate the site-effect to a higher aim as opposed to being a check on the analysis[77].

**Aim 1:** For hypothesis 1 (primary outcome), the outcome (frequency of IPV) will be analyzed under a clustered count regression framework (Poisson or Negative Binomial) with frequency as outcome, and time (6-weeks, 3-, 6- and 12 months,), group (ROSE, control) and time-by-group interaction, with the

baseline (BL) IPV frequency as the primary covariate. A generalized linear mixed models (GLIMMIX) approach will be adopted by means of a random subject intercept to account for the clustering within each participant. Changes over time within each group will be estimated post-hoc by sliced effects derived from the regression model with adjustment for multiple comparisons. In additional analysis, reduction in proportion of participants experiencing a binary outcome of  $IPV \geq 1$  days within the 90-day period will be analyzed using a clustered logistic regression with a dichotomous outcome, again with BL IPV frequency as a covariate.

**Aim 2:** Similar analyses will be conducted for the secondary outcomes of positive affect and well-being and for perceived emotional support (Aim 2a and 2b). For cost estimation (Aim 2c) see below.

**Aim 3:** The mediation tests will examine the ability of the proposed mediators, empowerment and self-efficacy, to account for all or part of the possible main effect of treatment on outcome. The mediators will be assessed at the end of treatment, and outcome will be taken from subsequent time points. We will use the product of coefficients test[78] to determine the magnitude and significance of mediated effects. This method multiplies the parameter estimate for the intervention predicting the mediator with the parameter estimate for the mediator predicting the outcome ( $\alpha\beta$ ). We will estimate the standard error and 95% confidence interval of  $\alpha\beta$  by bootstrapping, a re-sampling method that performs well when the assumption of normality may not hold.

**Missing Data:** Missing data will be handled by a weighted complete data analysis, using only complete cases after weighting the cases with the inverse probability of being missing. The probability is calculated as a function of the variables that are simultaneously associated with the outcome of interest and the event of being missing itself.

**Power:** We calculated the sample size using mean, standard deviation, and within-subject correlation estimates for IPV frequency from our R21 study. IPV frequency was measured by the CAS Total score. In our pilot data, we observed participants in ROSE demonstrated a significantly larger change in frequency of IPV than the control condition. The observed between-group effect size for change in IPV frequency at follow up was moderate to large: Cohen's  $d$  of 0.59 and 0.68 with and without adjustment for baseline score. Therefore, a more conservative effect size of  $d = 0.4$  was selected for sample size estimation. With four follow up IPV assessments, a within-subject correlation of 0.62, and a standard deviation of 20, 74 participants per group are needed to detect an effect size of  $d = 0.4$  for the overall intervention vs. control group difference with 80% power at the 5% significance level. A minimum effect size of  $d = 0.4$  will be detectable for the secondary outcomes of positive affect and well-being and perceived emotional support. The secondary outcome measures are reported as T-scores based on a normative mean of 50 and standard deviation of 10. With 74 patients per group and assuming an observed SD of 10, a 4-point difference in positive affect and well-being or perceived emotional support will be detectable. Moderate effect sizes (Cohen's  $f$  for multiple regression = 0.39) for mediated effects of the intervention ( $\alpha$  and  $\beta$ ) will be detectable with 80% power and 74 patients per group[79]. For all the outcomes, our proposed sample of 186 should be adequate for detecting small to moderate effect sizes. Even assuming the worst-case scenario of up to 20% drop-out in both the ROSE and control groups, we plan to recruit 93 participants per arm.

**Costs:** RAs, interventionist, training, and supervisory time will be priced based on actual salaries, plus fringe benefits and overhead (drawn from institutional records), with sensitivity analysis on salaries at average wage rates for job titles nationally based on Bureau of Labor Statistics (BLS) annual Occupation and Employment Survey (OES) data. Participant time will be priced at the participant's hourly wage, with the state minimum wage used to price time of those who are not presently employed. This pricing approach is widely accepted[80]. Because treatment as usual has no cost and the incremental costs of treatment are directly measurable, power to detect a difference is not a consideration; the standard error of the added costs can be calculated directly and cannot overlap with \$0. Data from different years will be adjusted to same-year dollars using the appropriate Employment Cost Index from BLS for wages and the Consumer Price Index for other costs. The cost-effectiveness ratio will be computed as number

of IPV incidents prevented divided by total cost. To judge the CEA estimate, we will compare it to the average cost of an IPV incident. Bid economist [name] is about to submit a manuscript updating IPV costs based on recent data and an amalgam of his prior estimates and estimates for the Centers for Disease Control[81,82]. Our cost of an IPV includes the quality-adjusted life years lost to the incident, so it can be used to estimate a second cost-effectiveness ratio, namely the cost per quality-adjusted life year saved. The numerator in that calculation is intervention costs minus the medical and other direct (criminal justice) costs of the incident. The IPV costs include lifetime costs related to medical care and criminal justice, converted to present value using the 3% discount rate recommended by the PCEHM[68]. We will use the Crystal Ball® add-in to Excel to bootstrap standard errors for the cost-effectiveness ratios. We also will conduct one-way sensitivity analyses on non-probabilistic parameters, notably the discount rate and the wage rates of the clinical staff. NB: a much larger sample would be needed to directly track the cost of the IPV incidents.

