## Objectives

In our R21 preliminary work, we demonstrated the feasibility and acceptability of ROSE, a computerized intervention for perinatal women with recent IPV who seek mental health treatment. In our pilot work, there were high ratings of satisfaction for ROSE. 100% completed the computerized intervention; 93% participated in the booster and 92% in the 4-month follow up assessment. Further, participants in the ROSE condition demonstrated a significantly larger change in frequency of IPV from baseline to follow-up (4 months after intake) than participants in the control condition ( $p < 0.007$ ).

The goal of this proposed study is to build upon these promising preliminary findings by testing whether ROSE reduces the frequency of IPV in a larger sample of perinatal women seeking mental health treatment, compare the effects of ROSE to an attention, time, and information matched control condition in two real-life clinical settings, examine the effects of the intervention for a more extended period of time, and include a cost estimate of ROSE. To achieve this, we propose a two-group, randomized controlled trial in which 186 perinatal women seeking mental health treatment are assigned to either (a) a computer-delivered, single-session brief intervention plus one interventionist-led phone booster; (ROSE); or (b) a computer-delivered control + one interventionist-led phone booster condition. Computer-delivered follow-up assessments will occur at 6-weeks, 3 months, 6 months, and 12 months after the baseline assessment. More specifically, we propose the following Specific Aims:

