## **2. STUDY DESIGN, METHODS, AND PROCEDURES**

### **Study Design**

Women (18 to 45 years old) presenting for an intake appointment at The Center for Women's Behavioral Health (WBH) at Women and Infants Hospital (WIH) and at The Perinatal Psychiatry Clinic (PPC) at the University of Michigan Health System (UMHS) will be screened for IPV victimization. Women who are pregnant or within 12 months postpartum – and report past 12-month history of IPV will be invited to participate in the study. At each site, those providing informed consent will be randomized either to an attention, time and information matched control condition or ROSE arm. Participants in both conditions will receive a phone booster within 4-weeks of their baseline assessment. Follow up assessments consisting of validated questionnaires will occur at 6-weeks after baseline assessment, and 3-, 6-, and 12 months, which will capture both immediate and sustained change and allow us to capture trajectories of IPV change. The booster session will be audio recorded so that adherence and competence ratings of the booster sessions can be conducted. These digital recordings which will be labeled with the study identification number and the booster session date and will be transferred to Women and Infants Hospital secure computer server via a secure server access. Access to the audio recordings will be limited to research staff. See "Sources of Materials" section for the assessments to be collected at each time point. If participants do not want to be audio recorded, they can still participate in the study.

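### A random intercept alone fixes one correlation for visits 7 to 46 weeks apart; if correlation falls with time, standard errors for long-gap change are too small, so prespecify robust ones.

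*Combined protocol and SAP*

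**What the plan says.** Section 4, Aim 1, specifies a Poisson or negative binomial mixed model with time (four follow-up visits), group, time-by-group and baseline IPV frequency. The only within-woman dependence enters "by means of a random subject intercept to account for the clustering within each participant". The same paragraph adds: "Changes over time within each group will be estimated post-hoc by sliced effects derived from the regression model with adjustment for multiple comparisons". Aim 2 says that the positive-affect and emotional-support outcomes will be analyzed similarly.

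The schedule, in Objectives, is: "Computer-delivered follow-up assessments will occur at 6-weeks, 3 months, 6 months, and 12 months after the baseline assessment". Study Design says that these visits "will capture both immediate and sustained change and allow us to capture trajectories of IPV change".

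The Power paragraph uses one correlation for every pair of visits: "With four follow up IPV assessments, a within-subject correlation of 0.62, and a standard deviation of 20, 74 participants per group are needed". It powers the overall difference between arms. The documents name no random slope, serial structure or robust standard error, and report no correlation by time between visits.

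**The concern.** A subject random intercept makes every pair of visits equally correlated on the model scale. Taking 3, 6 and 12 months as weeks 13, 26 and 52, the gaps between visits run from 7 weeks (6 weeks to 3 months) to 46 weeks (6 weeks to 12 months). Reports close together may well resemble each other more than reports most of a year apart.

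An average over visits is insensitive to this, but a difference between two visits is not: its standard error depends directly on the correlation of that pair. The time-by-group term and the within-arm changes are such differences, and they bear on whether an early effect is sustained, which is part of the stated reason for the visit schedule. The multiplicity adjustment does not repair a wrong standard error.

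**Working it through.** **Inputs.** Four follow-ups, correlation 0.62, SD 20, 74 per group, d = 0.4, 80% power, 5% level, 20% dropout (Power). Two-sided testing is assumed, because sidedness is not stated. The decay patterns are assumed.

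**The plan's own figure.** With equal correlation, the variance of a four-visit mean is (1 + 3 × 0.62)/4 = 0.715 of a single visit's. Then n = 2(1.960 + 0.842)²/0.4² × 0.715 = 98.1 × 0.715 = 70.2, so 71 per group, or 72 with the t distribution. The stated 74 is close and gives about 82% power. 74/0.80 = 92.5, so 93 per arm, as stated. The factor 0.715 depends only on the mean pairwise correlation, so decay around the same mean leaves the powered contrast unchanged.

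**Change contrasts, linear approximation with equal variances.** The true variance of a two-visit change is proportional to 2(1 − r), with r the correlation of that pair. The random-intercept model uses 2(1 − 0.62) for every pair. Hence true SE / model SE = √[(1 − r)/0.38], for within-arm change and for the arm difference in change alike.

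- 6 weeks to 12 months: r = 0.52 gives √(0.48/0.38) = 1.12; r = 0.39 gives √(0.61/0.38) = 1.27. The size of a nominal 5% test is P(|Z| > 1.96/1.12) ≈ 8% and P(|Z| > 1.96/1.27) ≈ 12%.
- 6 weeks to 3 months: r = 0.80 gives √(0.20/0.38) = 0.73; r = 0.87 gives √(0.13/0.38) = 0.59.

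The model SE for the arm difference in change is √(4 × 0.38 × 20²/74) = 2.87 for every pair. The table sets this against exponential decay in weeks with mean correlation 0.62. Its last two columns give the range over four calendar-time patterns: this one, two that combine a constant part with exponential decay, and a mild linear decline.

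| Pair | Gap (weeks) | r, exponential | True SE | Model/true SE, range | Size of 5% test |
|---|---|---|---|---|---|
| 6 wk–3 mo | 7 | 0.87 | 1.70 | 1.17–1.69 | 0.1–2% |
| 3–6 mo | 13 | 0.77 | 2.25 | 1.11–1.27 | 1–3% |
| 6 wk–6 mo | 20 | 0.66 | 2.70 | 1.01–1.06 | 4–5% |
| 6–12 mo | 26 | 0.59 | 2.99 | 0.94–0.99 | 5–6% |
| 3–12 mo | 39 | 0.45 | 3.45 | 0.83–0.91 | 7–10% |
| 6 wk–12 mo | 46 | 0.39 | 3.63 | 0.79–0.87 | 9–12% |

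The 3-degree-of-freedom time-by-group test has size 5.4% to 6.9%. With truly equal correlation, every ratio is 1.00.

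**Simulated negative binomial random-intercept fit** (3,000 runs, 74 per group), with exponential decay and with an equal-correlation control:

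| Contrast | Model/true SE, decay | Rejection, decay | Model/true SE, equal | Rejection, equal |
|---|---|---|---|---|
| 6 wk–3 mo | 1.16 | 2.4% | 0.98 | 5.9% |
| 3–6 mo | 1.06 | 4.0% | 0.95 | 5.7% |
| 6–12 mo | 0.92 | 6.8% | 0.94 | 6.3% |
| 3–12 mo | 0.88 | 8.5% | 0.95 | 6.2% |
| 6 wk–12 mo | 0.85 | 9.4% | 0.95 | 6.5% |
| Overall arm difference | 0.99 | 5.8% | 0.99 | 5.7% |

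The directions agree with the linear calculation, but the short-gap overstatement is smaller. Part of the long-gap inflation is present without decay (6.5% against 9.4%).

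A smaller simulation (350 null trials in each of two decay scenarios, mean 20, SD 20, average correlation about 0.5) gave 10.6% to 10.9% false positives for the arm difference in 6-week to 12-month change with model standard errors, and 5.4% with sandwich ones.

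**Poisson branch.** With an assumed mean count of 12, each visit-by-arm cell holds 74 × 12 = 888 events. The Poisson SE of the arm difference in log change is then about √(4/888) = 0.067, whatever the overdispersion. The actual spread in the negative binomial simulation was about 0.18 or more for every pair. If Poisson were chosen for overdispersed counts, standard errors would be too small at short gaps too.

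**The case against.** The best defence is that nothing in the documents shows decay. The plan gives one correlation, and the only pilot follow-up it reports is at 4 months, so lag-specific correlations cannot be derived. That stands: a reader might infer that the standard errors are simply wrong as planned, but they are wrong only if correlation falls with time.

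Three other inferences also go too far:

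- **Every adjacent pair is overstated.** The 6-to-12-month pair is adjacent but 26 weeks apart. Under calendar-time decay its standard error is about right or slightly small. It would be too large (ratio 1.21) only if correlation fell by visit number.
- **Time contrasts in general are falsely significant about twice as often as stated.** That fits only the longest gap. Short-gap contrasts are conservative outside the Poisson case, and the omnibus test is close to nominal.
- **The main conclusion is at risk.** The powered target is the overall arm difference, which the linear calculation and the negative binomial simulation both leave essentially unchanged. Aim 1 hypothesises lower IPV at each visit, which is a comparison between arms at single visits. The plan does not name the 6-week-versus-12-month contrast, and the within-arm changes are labelled post hoc and adjusted for multiplicity, so the unadjusted rates above are not the plan's operating rates.

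Other limits also stand. With 350 trials, 10.6% carries a Monte Carlo interval of roughly 7% to 14%, and that simulation had no equal-correlation control. The closed form assumes equal variances, whereas Protection against risk has follow-up CAS reports reach back to the preceding assessment (about 6, 7, 13 and 26 weeks), so variances may differ by visit and shift the ratios.

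None of this supplies evidence for equal correlation across 7 and 46 weeks, or a safeguard if it fails.

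**Conclusion.** The point holds as a conditional, inexpensive improvement, not as an error in the plan as written. If correlation falls with calendar time around a mean of 0.62, the 6-week to 12-month change is tested at about 8% to 12% instead of 5% in the linear calculation. The simulated negative binomial model gave 9.4%, against 6.5% with equal correlation. The 3-to-12-month change is affected less (7% to 10%). Early-change intervals are too wide in negative binomial or linear models; the simulated overstatement was 16% for 6 weeks to 3 months and 6% for 3 to 6 months.

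The result rests on the assumed decay, on equal variances in the closed form, and on the Power paragraph's 0.62 serving as the average correlation between follow-up visits. The linear figures bear most directly on the T-score outcomes of Aim 2.

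**What to change.** In Aim 1, and by reference in Aim 2, keep the mean model and random intercept, and state that all tests and confidence intervals will use empirical (sandwich) standard errors clustered by woman with a small-sample correction. The alternative is a serial-correlation term that depends on weeks between visits. The sandwich option also protects against unequal variances across visits and against overdispersion if Poisson is chosen. Fix the choice before outcome data are seen.

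The cost is about a sentence of text. Long-gap intervals become somewhat wider where the model standard error was too small (by the 1.12 to 1.27 factors if decay is that strong), and standard errors are slightly noisier if correlation is truly equal. The sample size need not change. Section 4 mentions GLIMMIX under Aim 1 but SPSS under Data checking, so confirm that the software actually used offers the chosen option.
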